### **Study Treatments**

All enrolled subjects receive 12 weeks of 200 mg PF-04965842 QD during the open-label run-in induction period. At the end of the 12 weeks, subjects responding to treatment as described above are randomized to receive double-blind maintenance treatment with 100 mg PF-04965842 QD, 200 mg PF-04965842 QD, or placebo (1:1:1 randomization ratio) for 40-weeks. In the event of flare during blinded treatment, subjects enter a 12-week open-label rescue period and receive 200 mg PF-04965842 QD with concomitant topical therapy per SOC.

### **Statistical Methods**

The statistical objective of the study is to characterize the loss of response with each randomized group after achieving response at Week 12 following open-label treatment with 200 mg PF-04965842 QD.

A total of 600 subjects with 200 receiving 100 mg PF-04965842 QD, 200 receiving 200 mg PF-04965842 QD, and 200 receiving placebo (1:1:1 randomization ratio) will provide 94% power to detect a ratio of median time to flare of at least 1.5 times between either dose of PF-04965842 (100 mg or 200 mg) and placebo. The Type I error rate is assumed to be 5% (2-sided). Assuming based on prior data, that about 44% of subjects would meet the protocol-defined criteria to be a responder at Week 12, approximately 1370 subjects would need to enter the open label run-in period of the study to ensure that 600 subjects are available for randomization.

There are six key hypotheses to be tested for each pairwise comparison between two PF-04965842 doses (200 mg QD and 100 mg QD) and placebo, for the primary and key secondary endpoints. For these hypotheses, the familywise Type-I error rate will be strongly controlled at 5% using a sequential, gatekeeping procedure.

For analysis of the primary and key secondary endpoints, a combination of graphical and analytical methods will be used. The time (in weeks) to protocol-defined flare will be used to evaluate the primary endpoint while the time (in weeks) to achieve an IGA score of  $\geq 2$  will be used for the key secondary endpoint. Subjects who do not report an event (protocol-defined flare or IGA  $\geq 2$ ) or discontinue the study during the double-blind randomized period will have their time to event censored at their last known visit in this period. Kaplan-Meier curves will be used to display the time to event and report the median time to event among the three randomized treatment groups. The log-rank test will be used to compare these curves. Proportions of subjects with an event and confidence intervals will also be reported by randomized treatment group.

In general, binary endpoints will be analyzed using the (Cochran-Mantel-Haenszel) test adjusted by randomization strata (age groups) and baseline disease severity. The difference between treatment groups in the proportion of subjects achieving a response along with its 95% confidence interval (using the normal approximation for the difference in binomial proportions) will be reported.

In general, for continuous endpoints, a mixed-effect model with repeated measures (MMRM) will be used. This model will include the factors (fixed effects) for treatment group, randomization strata (age groups) and baseline disease severity, visit, treatment-by-visit interaction, and relevant baseline value. Within the framework of MMRM, differences between groups will be tested using estimates from the MMRM model.

All subjects who receive investigational product (safety population) will be included in the safety analyses. All the safety data will be summarized descriptively through appropriate data tabulations, descriptive statistics, categorical summaries, and graphical presentations.

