### **5.2. Rescue Treatment**

Subjects will be instructed to contact the site if they experience a significant worsening of their atopic dermatitis, such as a recurrence of pruritus, during the double-blind treatment period. Site staff will determine if the subject should return to the site for an unscheduled (see [Section 6.5.1](#)) or regularly scheduled visit (see [Section 6.3](#)). Subject will be reminded not to take study drug on the day of the site visit. At the visit (regular or unplanned) the subject will be assessed for flare, defined as a loss of at least 50% of the EASI response at Week 12 and an IGA of 2 or higher. Subjects who meet the definition of flare are to receive rescue treatment that day and enter an open-label rescue period during which they receive 12-weeks of 200 mg PF-04965842 QD with concomitant topical therapy per SOC. See [Section 5.2.1](#) for guidance on topical therapies.

After completing the rescue period, subjects are allowed to enter the LTE study B7451015, if eligible. If a subject discontinues prematurely or is not eligible or willing to participate in B7451015, then the subject enters the 4-week, untreated follow-up safety period. Refer to [Schedule of Activities for Rescue Treatment](#).

Subjects not meeting the definition of flare will continue on their blinded treatment. Physicians may continue to clinically evaluate for flare using the EASI and IGA assessments at their discretion.

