requested by Pfizer Safety to obtain specific follow-up information in an expedited fashion. This information is more detailed than that recorded on the CRF. In general, this will include a description of the event in sufficient detail to allow for a complete medical assessment of the case and independent determination of possible causality. Any information relevant to the event, such as concomitant medications and illnesses, must be provided. In the case of a subject death, a summary of available autopsy findings must be submitted as soon as possible to Pfizer Safety. Any pertinent additional information must be reported on the CT SAE Report Form; additional source documents (eg, medical records, CRF, laboratory data) are to be sent to Pfizer Safety **ONLY** upon request.

Any clinically significant worsening of AD is considered an AE regardless of meeting the definition of flare.

As part of ongoing safety reviews conducted by the sponsor, any non-serious AE that is determined by the sponsor to be serious will be reported by the sponsor as an SAE. To assist in the determination of case seriousness, further information may be requested from the investigator to provide clarity and understanding of the event in the context of the clinical study.

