### 9.1. Sample Size Determination

A total of 600 subjects with 200 receiving PF-04965842 200 mg QD, 200 receiving PF-04965842 100 mg QD, and 200 receiving placebo (1:1:1 randomization) will provide 94% power to detect a ratio of median time to flare of at least 1.5 times between either dose of PF-04965842 (200 mg or 100 mg) and placebo. The Type I error rate is set at 5% (2-sided). Assuming based on prior data, that about 44% of subjects would meet the protocol-defined criteria to be a responder at Week 12, approximately 1370 subjects would need to enter the open label run-in period of the study to ensure that 600 subjects are available for randomization.

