### **9.2.4. Analysis of Secondary Endpoints**

In general, binary endpoints (such as EASI-50, EASI-90 or the proportion of subjects achieving  $\geq 4$  point improvement in severity of pruritus NRS measure) will be analyzed using the (Cochran-Mantel-Haenszel) test adjusted by randomization strata (age groups) and baseline disease severity. The difference between treatment groups in the proportion of subjects achieving a response along with its 95% confidence interval (using the normal approximation for the difference in binomial proportions) will be reported. If a subject withdraws from the study, then this subject will be counted as a non-responder for endpoints

after withdrawal. In addition, a subject in the FAS-RA subset who receives rescue treatment due to protocol-defined flare will be considered a non-responder.

For continuous endpoints, such as percent change from baseline in the EASI total score and BSA or change from baseline in SCORAD, PSAAD, DLQI/CDLQI, POEM, HADS, and change from baseline in the pruritus severity using the NRS measure, a mixed-effect model with repeated measures (MMRM) will be used. This model will include the factors (fixed effects) for treatment group, randomization strata (age groups), and baseline disease severity, visit, treatment-by-visit interaction, and relevant baseline value. Within the framework of MMRM, differences between groups will be tested using estimates from the MMRM model.

For all binary endpoints, missing data will be handled by considering subjects who withdraw or randomized subjects receiving rescue treatment as non-responders. No imputations will be made for continuous data and missing data will be considered to be MAR.

In general all secondary endpoints will be analysed for the FAS-RA subset. For the subjects requiring rescue therapy (FAS-RE subset), the response achieved at the end of the rescue period will be assessed in relation to the start of the rescue period. In addition to these two analysis sets, secondary endpoints will also be summarized for all subjects participating in the open-label run-in period (FAS-OL subset).

Hypotheses for all relevant secondary endpoints will be tested at the nominal 5% level of significance, without adjustments for multiple comparisons.

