5.3.3. Time to Event Endpoints

Subjects who reach the end of their accrual period without experiencing the event of interest will have their event times right censored at the end of their accrual period (ie, administrative censoring). Subjects who permanently discontinue before the end of their accrual period without experiencing the event of interest will have their event times considered missing.

For the primary analysis, these missing event times will be considered as right censored (censored at random) on their last date of dosing. As sensitivity analyses, tipping point analyses will be performed where these missing event times will be multiply imputed under an assumption of censoring not at random as proposed in Atkinson et al. (2019)¹ (see [Appendix 6](#)).

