When $\delta_1 = \delta_2 = 0$, we are in the CAR situation. For any other values of (δ_1, δ_2) , we have CNAR. In particular, when $\delta_1 = \delta_2 = 1$, we have a jump to reference situation where we assume that post-censoring, the hazard rate is no different from that in the placebo (reference) arm. We note also that this formulation assumes CAR for the placebo arm.

The corresponding survivor function $S^*(t; \beta^T x_i)$ is,

$$\begin{aligned} \log(-\log S^*(t; \beta^T x_i)) &= \beta_1 x_{i1} + \beta_2 x_{i2} + k \log t - k \log \theta, & t \leq C_i \\ &= \beta_1(1 - \delta_1)x_{i1} + \beta_2(1 - \delta_2)x_{i2} + k \log t - k \log \theta, & t > C_i \end{aligned}$$

The WPH model, as described in equation (1) above, will be used as the imputation model. Estimation of the model parameters will be performed under the Bayesian framework using Markov Chain Monte Carlo (MCMC) methods. We assign a non-informative prior for each component of $\beta = (\beta_0, \beta_1, \beta_2)$ to be independent and identically distributed as $\sim N(0, 10^6)$ and assign a weakly informative prior for the Weibull shape parameter $k > 0$ as an Inverse-Gamma distribution with shape= 10^4 and scale= 10^4 .

Let $\{\beta^b = (\beta_0^b, \beta_1^b, \beta_2^b), k^b: b = 1, 2, \dots, B\}$ be a sample (seed = 1848654157) from the posterior distribution. A single imputation \widetilde{T}_i^b of the unobserved (or censored) T_i is based on the posterior predictive distribution of the event times estimated from the WPH model. For example, if subject i is censored at C_i , \widetilde{T}_i^b must be sampled from the conditional distribution of $\widetilde{T}_i^b | \widetilde{T}_i^b > C_i$. This can be easily done by equating the conditional survivor function $S^*(t | t > C_i, \beta^{bT} x_i)$ to a uniform random variable and solving for t . Under our Weibull model, we draw $u_i \sim U[0, 1]$ and solve,

$$S^*(t_i | t_i > C_i, \beta^{bT} x_i) = \frac{S^*(t_i; \beta^{bT} x_i)}{S^*(C_i; \beta^{bT} x_i)} = u_i,$$

which has a simple closed form solution as,

$$\begin{aligned} k^b (\log t_i - \beta_0^b) \\ = \exp(\beta_1^b \delta_1 x_{i1} + \beta_2^b \delta_2 x_{i2}) \log \left\{ -\exp(-\beta_1^b x_{i1} - \beta_2^b x_{i2}) \log u_i + \left(\frac{C_i}{e^{\beta_0^b}}\right)^{k^b} \right\} \end{aligned}$$

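### No time-to-flare analysis counts stopping blinded treatment for worsening eczema short of the flare threshold as loss of response, and none can test the censoring of such exits on placebo

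*Protocol*

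**What the plan says.** **Primary analysis.** Protocol 9.2.3 and the Statistical Methods part of the Protocol Summary say that subjects who "discontinue the study during the double-blind randomized period will have their time to event censored at their last known visit in this period". SAP 5.3.3 covers permanent discontinuation without an event: "these missing event times will be considered as right censored (censored at random) on their last date of dosing". Neither text separates reasons for stopping. (The censoring dates also differ, last visit against last dose, and should be reconciled.)

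**Supportive analyses of time to flare (SAP 6.1.1.2).** There are two.
- The per-protocol set (SAP 4.2) keeps an unflared subject only if that subject completed the study.
- The tipping-point analysis imputes event times after censoring. Its model (SAP Appendix 6) contains treatment terms only, and the SAP adds: "We note also that this formulation assumes CAR for the placebo arm". The output it describes is hazard ratios.

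**Below the flare threshold.** Flare needs both an IGA of at least 2 and loss of at least half the Week 12 EASI response. Otherwise, "Subjects not meeting the definition of flare will continue on their blinded treatment" (Protocol 5.2). Medicated topicals are allowed only in the rescue period (Protocol 5.9). The protocol expects worsening of this kind: "Any clinically significant worsening of AD is considered an AE regardless of meeting the definition of flare" (8.1).

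**Other endpoints.** The key secondary endpoint is time to an IGA of 2 or more, with no EASI condition (SAP 3.2 and 6.2.1). For binary endpoints the rule is the reverse of censoring: "If a subject withdraws from the study, then this subject will be counted as a non-responder for endpoints" after that point (Protocol 9.2.4; likewise SAP 5.3.1).

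**The concern.** Leaving because eczema is returning is a weaker form of the event being measured. Take the protocol's own example: baseline EASI 40, Week 12 score 10, flare from 25 upwards. An EASI of 24 has lost 14 of 30 points, or 47% of the response. It is well above the entry minimum of 16, yet it is not a flare. If this subject stops, the Kaplan-Meier and log-rank methods assume the same future flare risk as for comparable subjects who stayed. That is doubtful here.

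The SAP's defence of missingness at random for continuous endpoints (5.3.2) is that dropout depends on EASI and IGA values already observed, which the mixed model uses. That defence does not carry over. The log-rank test is stratified, and the Cox model adjusted, only for age group and severity at study baseline (SAP 5.2.4). Neither uses EASI or IGA after randomization.

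At stake are the flare-free probabilities at Week 52 and the three pairwise contrasts, including 200 mg against 100 mg.

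**Working it through.** **Which planned analysis counts such an exit as loss of response?**

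| Analysis | Treatment of an unflared exit for worsening |
|---|---|
| Time to flare, primary | Censored at random |
| Time to flare, per-protocol | Removed |
| Time to flare, tipping point | Event time imputed regardless of reason; placebo stays censored at random |
| Key secondary, IGA of 2 or more | Event, if that IGA was recorded in the blinded period |
| Binary endpoints | Non-responder at later visits |

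So the gap is confined to time to flare. The key secondary can still miss a subject who leaves without an assessment, or whose IGA first reaches 2 at a termination visit after the last dose: its window ends at the last randomized dose, while that visit may fall up to a week later (Protocol 6.6). Its only supportive analysis is per-protocol (SAP 6.2.1.2).

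**The plan's own figure.** 200 per arm "will provide 94% power to detect a ratio of median time to flare of at least 1.5 times between either dose of PF-04965842", two-sided 5% (Protocol 9.1). With proportional hazards the ratio 1.5 is a hazard ratio of 1/1.5 = 0.667. Schoenfeld's formula gives

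events = 4 × (1.960 + 1.555)² / (ln 1.5)² = 301 of 400.

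The documents state no event count, median or dropout rate, so 94% cannot be derived from them. An assumed exponential placebo median of 16 weeks over 40 blinded weeks gives 302 events and 94.1%. That median was chosen because it fits; medians of 12 and 24 weeks give 96.1% and 88.7%.

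**Illustration.** Weekly hazards are ln 2/16 = 0.0433 on placebo and 0.0433/1.5 = 0.0289 on drug. Suppose a share q of would-be flares leaves just before threshold and is censored. Then

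- observed hazard ratio = 0.667 × (1 − q_drug)/(1 − q_placebo);
- Kaplan-Meier flare-free at Week 52 = exp(−40 × hazard × (1 − q));
- power = Φ(√events/2 × |ln HR| − 1.96).

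| q placebo / drug | Hazard ratio | Flares | Power | Flare-free, placebo | Flare-free, drug |
|---|---|---|---|---|---|
| 0 / 0 | 0.667 | 302 | 94% | 17.7% | 31.5% |
| 5% / 2.5% | 0.684 | 290 | 90% | 19.3% | 32.4% |
| 10% / 5% | 0.704 | 278 | 83% | 21.0% | 33.4% |
| 20% / 10% | 0.750 | 255 | 63% | 25.0% | 35.4% |
| 10% / 10% | 0.667 | 271 | 92% | 21.0% | 35.4% |
| 5% / 10% | 0.632 | 280 | 97% | 19.3% | 35.4% |

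In the 10%/5% row: 0.667 × 0.95/0.90 = 0.704; flares = 200 × 0.90 × 0.823 + 200 × 0.95 × 0.685 = 278; √278.3/2 × 0.351 − 1.96 = 0.97, hence 83%. The higher power in the last row is not a gain: it reflects a contrast that censoring has flattered. Counting the exits as events returns the first row.

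This model makes every exit an imminent flare, so for given shares it is the extreme case. If exits carry no information about flare risk, the flare hazard ratio and flare-free rates are not distorted.

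**How far the tipping point helps.** Under jump to reference with the same hazards, a drug-arm subject stopping 4 weeks into blinded treatment is imputed a flare by Week 52 with probability 1 − exp(−0.0433 × 36) = 79%, against 1 − exp(−0.0289 × 36) = 65% under censoring at random. The exit is counted in part. For placebo the probability cannot be changed.

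**The case against.** A reader might infer that no planned analysis treats these subjects as having lost response. The documents do not support that. Every subject is randomized at IGA 0 or 1, so a subject whose IGA has risen to 2 or 3 is an event on the key secondary endpoint once it is recorded. A subject assessed for flare and refused rescue normally has that IGA on file. That endpoint is in the familywise-controlled sequence for all three comparisons, and setting it beside the primary result shows something of how much worsening falls short of flare.

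A reader might also take the tipping point to do no more than pull the drug arms toward placebo. Appendix 6 lets the two parameters vary separately and states no cap, so drug-arm dropouts can be given a hazard worse than placebo's and the 200 mg against 100 mg contrast is stressed too. That covers the direction that would flatter the drug. Exits commoner on placebo shrink the effect, which is conservative.

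The incentive to leave should not be overdrawn either. A subject who stays can be reassessed for flare at the physician's discretion, antihistamines and emollients are permitted, and one who discontinues goes into untreated follow-up. Finally, the primary endpoint is loss of response requiring rescue; counting an investigator-attributed exit makes a softer composite.

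All of this stands, and it is why the addition should be supportive only. It leaves three things untested: the reason for leaving, placebo exits, and the Week 52 flare-free probabilities.

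**Conclusion.** The concern holds as a partial gap. Time to flare censors every unflared discontinuation at random whatever the reason. No time-to-flare analysis counts leaving for worsening eczema as loss of response, and none can vary the assumption on placebo.

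A reader might conclude that the primary results are biased. The documents do not establish that. If such exits predict imminent flare, flare-free probabilities may be overstated in every arm. The hazard ratio may move toward 1 (exits commoner on placebo), in the drug's favour (commoner on drug), or not at all (equal shares in this model). With shares of 5% to 10% of would-be flares the illustration gives hazard ratios from 0.63 to 0.70 around 0.667, and flare-free rates about 2 to 4 points too high. These rest on constant hazards, a placebo median fitted to the stated power, no other loss to follow-up, and exit shares that the documents do not give. The actual size is unknown. This is a low-cost improvement and no reason to change the primary analysis.

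**What to change.** Add to SAP 6.1.1.2, with a line in 5.3.3, a pre-specified supportive analysis in the randomized full analysis set, for all three arms and all three pairwise comparisons. In it:

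- permanent discontinuation of blinded treatment for insufficient response or worsening atopic dermatitis (by disposition reason, or by an adverse event of worsening that led to discontinuation) counts as loss of response on the last dose date;
- all other discontinuations stay censored;
- the hazard ratio and Week 52 event-free probability are shown beside the primary result.

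The primary analysis, the testing sequence and alpha stay as they are. The cost is one SAP paragraph and one more run of the same log-rank, Cox and Kaplan-Meier programs. No new data are needed: Protocol 8.1 records clinically significant worsening as an adverse event, 8.1.3 distinguishes withdrawals due to adverse events on the case report form, and SAP 6.6.2 already summarizes discontinuations. The drawback is that the reason for leaving is investigator-reported, though it is recorded under the blind.

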### SCHEDULE OF ACTIVITIES FOR RUN-IN AND BLINDED TREATMENTS

The schedule of activities table provides an overview of the protocol visits and procedures. Refer to the [STUDY PROCEDURES](#) and [ASSESSMENTS](#) sections of the protocol for detailed information on each procedure and assessment required for compliance with the protocol.

The investigator may schedule visits (unplanned visits) in addition to those listed on the schedule of activities table, in order to conduct evaluations or assessments required to protect the well-being of the subject.

Visit Identifier	Day -28 a Screening	Day 1 Week 0 Baseline	Day 8 Week 1 Call	Day 15 Week 2	Day 29 Week 4	Day 43 Week 6 Call	Day 57 Week 8	Day 85 Week 12 Randomize Responders	Day 113 b Week 16	Day 197 b Week 28	Day 281 b Week 40	Day 365 b Week 52 EOT/ET	EOS, Follow-up Week 56/ 4 Weeks post ET
	Visit 1	Visit 2	Visit 3	Visit 4	Visit 5	Visit 6	Visit 7	Visit 8	Visit 9	Visit 10	Visit 11	Visit 12	Visit 13
Visit Window	None	None	±1 Day	±1 Day	±2 Days	±3 Days	±3 Days	±3 Days	±3 Days	±7 Days	±7 Days	±3 Days	±3 Days
Enrollment Procedure													
Informed consent c	X												
Register subject using IRT system	X												
Inclusion/Exclusion Criteria	X	X						X					
C-SSRS d	X	X					X	X	X	X	X	X	X
SBQ-R d	X												
PHQ-8 d	X												
Demographics, Medical History, Tobacco and Alcohol History, Atopic Dermatitis Disease History e	X												
Review Prior/Concomitant Medications & Treatments	X	X	X	X	X	X	X	X	X	X	X	X	X
Dispense e-Diary and instruct subjects on use	X												
Provide Patient Emergency Contact Card	X												
Medical Procedures													
Complete Physical Exam f	X	X						X				X	
Targeted Physical Exam f				X	X		X		X	X	X		X
Vital Signs g	X	X		X	X		X	X	X	X	X	X	X
Weight/Height dd	X	X						X				X	

Visit Identifier	Day -28 a Screening	Day 1 Week 0 Baseline	Day 8 Week 1 Call	Day 15 Week 2	Day 29 Week 4	Day 43 Week 6 Call	Day 57 Week 8	Day 85 Week 12 Randomize Responders	Day 113 b Week 16	Day 197 b Week 28	Day 281 b Week 40	Day 365 b Week 52 EOT/ET	EOS, Follow-up Week 56/ 4 Weeks post ET
	Visit 1	Visit 2	Visit 3	Visit 4	Visit 5	Visit 6	Visit 7	Visit 8	Visit 9	Visit 10	Visit 11	Visit 12	Visit 13
Visit Window	None	None	±1 Day	±1 Day	±2 Days	±3 Days	±3 Days	±3 Days	±3 Days	±7 Days	±7 Days	±3 Days	±3 Days
ECG (12-lead) kk	X	X		X	X		X	X	X	X	X	X	X
Laboratory Assessments h													
Hematology i	X	X		X	X		X	X	X	X	X	X	X
Coagulation Panel j	X	X		X	X		X	X	X	X	X	X	X
Serum chemistry k	X	X		X	X		X	X	X	X	X	X	X
Urinalysis l	X	X		X	X		X	X	X	X	X	X	X
Lipid Panel m		X			X			X				X	X
Serum FSH (post-menopausal) or Pregnancy Test n	X												
Urine Pregnancy Test (conducted at study site) o		X		X	X		X	X	X	X	X	X	X

HIV Testing q	X												
Hepatitis B Surface Antigen (HBsAg), Hepatitis B Surface Antibody (HBsAb), Hepatitis B Core Antibody (HBcAb), Hepatitis C Antibody (HCV Ab), Hepatitis C Viral RNA (HCV RNA) r	X												
HBV DNA testing for China and Taiwan ll	X							X		X	X	X	
Varicella Zoster Virus (VZV IgG Ab) (adolescents only, if applicable) s	X												
Tuberculosis Test t	X											X ii	
Chest X-ray hh	X											X ii	

Visit Identifier	Day -28 a Screening	Day 1 Week 0 Baseline	Day 8 Week 1 Call	Day 15 Week 2	Day 29 Week 4	Day 43 Week 6 Call	Day 57 Week 8	Day 85 Week 12 Randomize Responders	Day 113 b Week 16	Day 197 b Week 28	Day 281 b Week 40	Day 365 b Week 52 EOT/ET	EOS, Follow-up Week 56/ 4 Weeks post ET
	Visit 1	Visit 2	Visit 3	Visit 4	Visit 5	Visit 6	Visit 7	Visit 8	Visit 9	Visit 10	Visit 11	Visit 12	Visit 13
Visit Window	None	None	±1 Day	±1 Day	±2 Days	±3 Days	±3 Days	±3 Days	±3 Days	±7 Days	±7 Days	±3 Days	±3 Days
Pharmacokinetic													
Pharmacokinetic Blood Sampling (Post-dose) u								X					
Trial Treatment													
Randomization								X					
Drug Dispensing		X			X		X	X	X	X	X		
Investigational Product Accountability				X	X		X	X	X	X	X	X	
Investigational Treatment Administration v		X-----X											
Review eDiary to assess completion			X	X	X	X	X	X	X	X	X	X	
Assess eligibility for B7451015 w								X				X	
Clinical Assessments													
Fitzpatrick Skin Type Assessment		X											
Investigator's Global Assessment (IGA)	X	X		X	X		X	X	X	X	X	X	X
SCORing Atopic Dermatitis (SCORAD)	X	X		X	X		X	X	X	X	X	X	X
Eczema Area and Severity Index (EASI)	X	X		X	X		X	X	X	X	X	X	X
Total Body Surface Area (BSA from EASI)	X	X		X	X		X	X	X	X	X	X	X
Patient-reported Outcome													
Pruritus Numerical Rating Scale -eDiary (NRS) x	X-----X	X-----X		X			X	X	X	X	X	X	X
Patient Global Assessment (PtGA)		X		X	X		X	X	X	X	X	X	X
Dermatology Life Quality Index (DLQI or CDLQI) y		X		X	X		X	X	X	X	X	X	X

Visit Identifier	Day -28 a Screening	Day 1 Week 0 Baseline	Day 8 Week 1 Call	Day 15 Week 2	Day 29 Week 4	Day 43 Week 6 Call	Day 57 Week 8	Day 85 Week 12 Randomize Responders	Day 113 b Week 16	Day 197 b Week 28	Day 281 b Week 40	Day 365 b Week 52 EOT/ET	EOS, Follow-up Week 56/ 4 Weeks post ET
	Visit 1	Visit 2	Visit 3	Visit 4	Visit 5	Visit 6	Visit 7	Visit 8	Visit 9	Visit 10	Visit 11	Visit 12	Visit 13
Visit Window	None	None	±1 Day	±1 Day	±2 Days	±3 Days	±3 Days	±3 Days	±3 Days	±7 Days	±7 Days	±3 Days	±3 Days
Patient-Oriented Eczema Measure (POEM)		X		X	X		X	X	X	X	X	X	X
Hospital Anxiety and Depression Scale (HADS)		X		X	X		X	X	X	X	X	X	X
Pruritus and Symptoms Assessment for Atopic Dermatitis - eDiary (PSAAD) z	X-----X	X-----X											
EQ-5D-5L (adults) or EQ-5D-Y (ages 12-17 years) aa		X		X	X		X	X	X	X	X	X	X
SF-36v2, Acute bb (adults)		X						X				X	X
FACIT-F (adults) or Peds-FACIT-F (ages 12-17 years) cc		X						X				X	X
Asthma Control Questionnaire (ACQ) for all subjects with a prior diagnosis of asthma		X						X				X	X
Safety													
Serious and non-serious adverse event monitoring	X →	→	→	→	→	→	→	→	→	→	→	→	→ X
Assess for presence of flare ee									X	X	X	X	
Contraception Check ff	X	X	X	X	X	X	X	X	X	X	X	X	X
Serum Sample for Baseline Viral Screen gg		X											

Abbreviations: ACQ = Asthma Control Questionnaire; BSA = body surface area; CDLQI = Children's Dermatology Life Quality Index; C-SSRS = Columbia Suicide Severity Rating Scale; DLQI = Dermatology Life Quality Index; EASI = Eczema Area and Severity Index; ECG = electrocardiogram; EOS=End of Study; EOT = End of Treatment; ET= early termination; EQ-5D-5L = EuroQol Quality of Life 5-Dimension 5-Level Scale; EQ-5D-Y = EuroQol Quality of Life 5-Dimension, Youth Scale; FACIT-F = Functional Assessment of Chronic Illness Therapy Fatigue Scale; FSH = follicle stimulating hormone; GGT = gamma-glutamyl transferase; HADS= Hospital Anxiety and Depression Scale; HBsAg = hepatitis B surface antigen; HBsAb = hepatitis B surface antibody; HBcAb = hepatitis B core antibody; HBV DNA = hepatitis B virus deoxyribonucleic acid; HCVAb = hepatitis C antibody; HCV RNA = Hepatitis C Viral RNA; Hep B = Hepatitis B; HIV = human immunodeficiency virus; HSV-1 = herpes simplex virus type 1; HSV2 = herpes simplex virus type 2; IGA = Investigator's Global Assessment; IgE = Immunoglobulin E; IRT = Interactive Response System; LDH = Lactate dehydrogenase; LLQ = lower limit of quantification; MCH = mean corpuscular hemoglobin; MCHC = mean corpuscular hemoglobin concentration; MCV = mean corpuscular volume; NK = Natural Killer; NRS = numerical rating scale; Peds-FACIT-F = Pediatric Functional Assessment of Chronic Illness Therapy Fatigue Scale; PHQ-8 = Patient Health Questionnaire 8 items; POEM= Patient-Oriented Eczema Measure; PSAAD=Pruritus and Symptoms Assessment for Atopic Dermatitis; PtGA = Patient Global Assessment; RBC = Red blood cell; RNA = Ribonucleic acid; SBQ-R = Suicide Behaviors Questionnaire-Revised; SCORAD = SCORing Atopic Dermatitis; SF-36v2 = Short Form-36 Health Survey Version 2;VZV = varicella zoster virus; VZV IgG Ab = varicella zoster virus immunoglobulin G antibody.

- a. Day relative to start of study treatment (Day 1).
- b. From Day 86 through Day 365, if the subject flares as defined by protocol, begin rescue treatment period. See [Schedule of Activities for Rescue Treatment](#).
- c. Obtain written informed consent; for subjects aged under the legal age of majority (legal adulthood) in the subject's country, obtain written informed consent from legally acceptable representative/parent(s) or legal guardian, and informed assent from the patient (if age appropriate according to local regulations).
- d. Site staff is to administer the C-SSRS, SBQ-R and PHQ-8 to all subjects at screening and score immediately. Subjects who have recent or active suicidal ideation or behavior or clinically significant depression will be excluded from the study or discontinued from the study per [Section 4.2](#), [Section 7.5.1](#), [Section 7.5.2](#) and [Section 7.5.3](#). Subjects meeting exclusionary results on the C-SSRS, SBQ-R and PHQ-8 should be excluded from participation; it is recommended the subject's primary care physician (PCP) should be informed, and the subject referred to a mental health professional, either by the PCP or the investigator according to their usual practice. Post-screening, if there are "yes" answers on items 4, 5 or on any behavioral question of the Since Last Visit C-SSRS a risk assessment by a qualified mental health professional (MHP) should be done to determine whether it is safe for the subject to continue to participate in the trial.
- e. Atopic Dermatitis Disease History includes collection of details of AD: AD diagnosis and duration, the use of topical treatments, systemic treatments and other treatments for AD.
- f. Complete physical examinations must be performed by the investigator, sub investigator or a qualified health professional per local guidelines. Complete physical examinations consist of assessments of general appearance; skin; head, eyes, ears, nose and throat (HEENT); mouth, heart; lungs; breast (optional); abdomen; external genitalia (optional); extremities; neurologic function; and lymph nodes. Targeted physical examinations must be performed by the investigator, sub-investigator or a qualified health professional per local guidelines and should include skin, heart, lungs, and abdomen and examination of body systems where there are symptom complaints by the subject.
- g. Vital Signs include sitting blood pressure, pulse, respiratory rate, and temperature measured after at least 5 minutes of rest.
- h. Laboratory tests with abnormal results (per [Section 6.1](#) and [Section 7.6.2](#)) may be repeated once during the screening period; the last value will be used to determine eligibility.

- i. Hematology includes: Hemoglobin, hematocrit, red blood cell count and indices (MCH, MCHC, MCV, RBC Morphology), white blood cells, neutrophils (%), lymphocytes (%), monocytes (%), eosinophils (%), basophils (%), platelets, reticulocyte count, lymphocyte subsets and markers (Total T cells [CD3+], CD4+ T cells [CD3+CD4+], CD8+ T cells [CD3+CD8+], NK cells [CD3- CD16+CD56+], B cells [CD3-CD19 +).
- j. Coagulation panel includes: Activated Partial Thromboplastin Time (APTT), Prothrombin Time/International Normalized Ratio (PT/INR).
- k. Serum chemistry includes: blood urea nitrogen (BUN), serum creatinine, creatine phosphokinase, glucose, Ca++, Na+, K+, Cl, total CO2, aspartate aminotransferase (AST), alanine aminotransferase (ALT), gamma-glutamyl transferase (GGT), total, indirect and direct bilirubin, alkaline phosphatase, lactate dehydrogenase, uric acid, albumin and total protein.
- l. Urinalysis includes: pH, Glucose (qualitative), Protein (qualitative), Blood (qualitative), Ketones, Nitrites, Leukocyte esterase, Microscopy and/or culture (performed as appropriate).
- m. Lipid Panel includes: total cholesterol, low-density lipoprotein (LDL), high-density lipoprotein (HDL), and triglycerides. A minimum of 8-hour fasting is required for lipid profile evaluation at Day 1, Week 4, Week 12, Week 52 and EOS visits.
- n. Serum pregnancy testing at screening is required for women of childbearing potential including adolescents aged 12 years and older regardless of whether they have experienced menarche. Follicle stimulating hormone (FSH) test to be performed at Screening to confirm postmenopausal status in female subjects who have been amenorrheic for at least 12 consecutive months.
- o. Urine pregnancy test must be performed at every site visit prior to dosing with the investigational product for female subjects of childbearing potential including adolescents aged 12 years and older regardless of whether they have experienced menarche.
- 
- q. Subjects testing positive for HIV will be screen-failed.
- r. HBsAb reflex testing will be performed only if HBsAg negative but HbCAb positive. Subjects who are positive for HCVAb and HCV RNA will be screen-failed.
- s. VZV IgG antibody testing is required to confirm eligibility in adolescent subjects who have not received at least one dose of a varicella vaccine.
- t. A documented TB test performed within 12 weeks prior to Day 1 is acceptable. Subjects with a history of tuberculosis may not require TB testing as per the protocol exclusion criteria in [Section 4.2](#). Perform TB test procedure using the QuantiFERON®-TB Gold In Tube Test (or Purified Protein Derivative). A negative PPD test can be substituted for the QuantiFERON®-TB Gold In-Tube test only if the central laboratory is unable to perform the QuantiFERON®-TB Gold In-Tube test or cannot determine the results to be positive or negative and the Pfizer Medical Monitor approves it on a case-by-case basis. In addition to protocol required TB testing, sites should follow their local standards for TB status determination, which may include chest X-ray. See [Section 7.3.4](#).
- u. A PK blood sample will be collected at 2.0 hours (±30 min) postdose of open-label study drug (200 mg) at the Week 12 visit. For Early Termination (ET) visits, if the subject discontinues before Week 4, do not collect a PK sample. If the ET visit occurs at or after Week 4 and before Week 12, collect a PK sample only if the subject takes the investigational product at the site visit.

- v. Subjects should take the medication from study Days 1 to 365. Subjects will be encouraged to take the medication in the morning whenever possible; however, at study visit days, subjects are to be instructed to refrain from dosing at home and are to take the dose in the clinic. Instruct subjects regarding proper storage conditions for investigational product on Day 1.
- w. Subjects who are non responders but complete the 12 week run-in treatment and subjects who are responders at EOT will be assessed for eligibility for participation in long-term extension study B7451015 as noted in [Section 6.3.5](#).
- x. Pruritus Numerical Rating Scale (NRS) will be assessed using an eDiary daily during the screening period and from Study Day 1 to 15. After Day 15, the Pruritus NRS will be completed only on study visit days in the eDiary. At the Screening visit, site staff will dispense the electronic tablet (ePRO device) and review instructions for completion of the subject eDiary for the NRS. At every visit, the study coordinator will review the eDiary for completeness and counsel the subject on how to complete the items in the daily eDiary, if needed.
- y. DLQI will be completed by adult subjects only. Adolescents 12-17 years of age will complete the CDLQI instead.
